2.3 ANALYSIS POPULATIONS

The randomized population includes any patient who has been allocated to a randomized treatment regardless of whether the treatment kit was used.

Patients treated without being randomized will not be considered randomized and will not be included in any efficacy population.

For any patient randomized more than once, only the data associated with the first randomization will be used in any analysis population. The safety experience associated with any later randomization will be assessed separately.

The safety experience of patients treated and not randomized will be reported separately, and these patients will not be in the safety population.

2.3.1 Efficacy populations

The primary analysis population will be the ITT population as defined in [Section 2.3.1.1](#).

2.3.1.1 Intent-to-treat population

The intent-to-treat (ITT) population is the randomized population analyzed according to the treatment group allocated by randomization.

2.3.2 Safety population

The safety population is defined as randomized population who received at least 1 dose or part of a dose of the SC IMP, analyzed according to the treatment actually received. In addition:

- Nonrandomized but treated patients will not be part of the safety population; however, their safety data will be presented separately
- Randomized patients for whom it is unclear whether they took the IMP will be included in the safety population as randomized
- For patients receiving more than one SC IMP during the trial, the treatment group allocation for as-treated analysis will be the treatment group for which the patient received the majority of doses. In such cases, individual patient listings will be provided for each treatment group with treatment start and end date for each treatment exposed.

2.3.3 Pharmacokinetics and ADA populations

The PK population will consist of all patients in the safety population with at least one post-dose, non-missing serum sarilumab concentration value. The ADA population will consist of all patients in the safety population with at least one post-dose, evaluable ADA sample. Patients will be analyzed according to the treatment actually received.

2.3.4 Population with and without trial impact (disruption) due to COVID-19

The population without trial impact (disruption) due to COVID-19 is defined as patients without any critical or major deviation related to COVID-19 or did not permanently discontinue study treatment due to COVID-19. Population with trial impact due to COVID-19 are patients with any critical or major deviation related to COVID-19 or permanently discontinue study treatment due to COVID-19. These populations will be used to summarize treatment exposure, treatment compliance, subgroup analysis of primary endpoint and safety only if > 10% patients are impacted by the COVID-19 pandemic.

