1 OVERVIEW AND INVESTIGATIONAL PLAN

This statistical analysis plan (SAP) provides a comprehensive and detailed description of statistical strategy and methodology to be used to analyze the data from sarilumab EFC15160 study in patients with active polymyalgia rheumatica (PMR).

Due to the ongoing pandemic of COVID-19 (the disease caused by the novel coronavirus), the operations of sarilumab (Kevzara®) clinical trial EFC15160 have been significantly disrupted in various countries and sites. Consequently, the screening/recruitment activities for this study have been suspended since March 2020. Due to the protracted recruitment timeline and internal portfolio reprioritization, in July 2020, Sanofi decided not to re-open the screening/recruitment activities and to discontinue the study. This decision is not related to any safety issues arising from the administration of sarilumab.

A total of 118 patients (out of 280 planned patients) have been randomized in the study. Despite the decision to discontinue the study, all patients already recruited will be allowed to continue in the study to complete the 52-week treatment period and the 6 weeks post-treatment follow up per protocol.

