1.6 STATISTICAL MODIFICATIONS MADE IN THE STATISTICAL ANALYSIS PLAN

Due to the premature termination of the study, a total of 118 patients (42%) of the 280 patients planned were randomized. The randomized patients could continue in the study to complete the treatment period and the 6 weeks post-treatment follow up per protocol. Hence, there are no changes to the efficacy analysis plan per protocol.

The COVID-19 pandemic has also impacted data collection as patients may not be able to visit clinical sites for endpoint assessments. Additional patient level information at visits that were impacted by the pandemic situations were captured for assessments performed in visits that were delayed, not done, partially done on site, or partially done by phone. Major or critical COVID-19 impacted deviations per protocol were also recorded.

To assess the impact of the pandemic on the study, COVID-19 related summaries are added as below.

- a) Patients who permanently discontinue study treatment or study due to COVID-19 reasons will be summarized in patient disposition table
- b) Patient disposition by visit according to trial impact due to COVID-19
- c) Critical or major deviations summary according to COVID-19 impact
- d) Number (%) of patients experiencing at least one treatment-emergent COVID-19 related adverse event by primary SOC and PT

In addition, if > 10% patients are impacted by the COVID-19 pandemic, below summaries/analyses will be generated by COVID-19 impacted population (Yes, No):

- a) Extent of exposure to SC IMP
- b) Treatment compliance for SC IMP

- c) Number (%) of patients with TEAEs by primary SOC and PT, and
- d) Analysis of the primary endpoint of sustained remission at Week 52.

The population with and without trial impact (disruption) due to COVID-19 is defined in [Section 2.3.4](#).

In addition, upon meeting with Japan Health Authorities (PMDA) in April 2019, data for the components to calculate the PMR activity score (PMR-AS) were subsequently collected and the analysis plan is described in [Section 2.4.4.3](#).

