Tipping point analysis will be performed. The number of responders to impute in each treatment group will vary from zero to up to the total number of patients with missing primary endpoint outcomes. For each imputation combination, a p-value based on Fisher's exact test will be calculated. The goal is to identify scenarios leading to non-significant results (p-value ≥ 0.05).

Patients who receive rescue therapy will be considered as non-responders. Withdrawn patients who had a disease flare prior to withdrawal will also be considered as non-responders as this represents the true outcome had they remained in the study. Withdrawn patients who did not experience a disease flare prior to withdrawal will be considered as missing and will be sequentially imputed for the tipping point analysis.

Subgroup analyses: To assess the consistency in treatment effects across subgroup levels, subgroup analyses will be conducted for the primary endpoint with respect to:

- Gender (Male versus Female)
- Race (Caucasian/White versus all other races)
- Region (Region 1 [Western countries], Region 2 [South America], Region 3 [Rest of the world])
- Age (<70, ≥ 70)
- Baseline weight (<60, ≥ 60 and <100, ≥ 100 kg)
- BMI (<25, ≥ 25 and <30, ≥ 30 kg/m²)
- Baseline CRP (\leq median, >median)
- Baseline ESR (\leq median, >median)
- Baseline CS dose (\leq median, >median)
- Number of relapses prior to screening (1, > 1 relapse)
- COVID-19 impacted population (Yes, No) – will only be performed if >10% of patients were impacted by COVID-19. The population without trial impact (disruption) due to COVID-19 is defined as patients without any critical or major deviation related to COVID-19 or did not permanently discontinue study treatment due to COVID-19.

Within each subgroup, the number and proportion of patients achieving sustained remission at Week 52 by treatment groups will be presented together with the proportion difference between sarilumab and placebo groups and its 95% confidence interval.

Subgroup analyses will also be performed with logistic regression models for binary status of patients achieving sustained remission at Week 52, with treatment group, subgroup variable and the subgroup-by treatment interaction as covariates. A p-value for the test of interaction will be provided.

Forest plots of treatment differences (proportion difference) between sarilumab and placebo at Week 52 and corresponding CIs for each subgroup will be provided.

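### The SAP's population without COVID-19 impact is not the complement of its population with impact, so a patient meeting exactly one criterion falls in both

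*SAP*

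**What the plan says.** SAP section 2.3.4 defines two populations. The one without impact is "patients without any critical or major deviation related to COVID-19 or did not permanently discontinue study treatment due to COVID-19". The one with impact is "patients with any critical or major deviation related to COVID-19 or permanently discontinue study treatment due to COVID-19". The subgroup list in section 2.4.4.1 repeats the first definition in the same words and does not restate the second.

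Section 1.6 and the subgroup list both treat COVID-19 impact as one variable with the levels Yes and No. Section 2.4.4.1 also plans a logistic model for every subgroup factor, "with treatment group, subgroup variable and the subgroup-by treatment interaction as covariates".

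The populations feed four sets of outputs: exposure to the injected study drug, compliance with it, treatment-emergent adverse events by system organ class and preferred term, and the primary endpoint by subgroup. Section 2.3.4 allows their use "only if > 10% patients are impacted by the COVID-19 pandemic". Sections 1.6, 2.4.4.1 and 2.4.5.1 carry the same condition. Section 2.4.3 lists exposure and compliance in these populations without repeating it.

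**The concern.** A Yes/No split needs each patient in exactly one group. The opposite of meeting either criterion is meeting neither. The SAP instead asks only that one of the two criteria be absent, so a patient with a major COVID-19 deviation who stayed on treatment qualifies as unaffected while also qualifying as affected. The same happens in mirror image to a patient who stopped treatment because of COVID-19 but has no critical or major deviation.

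The purpose of the split is to show whether pandemic disruption changed exposure, safety or the primary result. If the definitions were programmed as they stand, the unaffected column would contain most or all of the patients it is meant to leave out, and the comparison would be blurred. The descriptive tables could be printed that way without any error message. The interaction model could not be fitted at all, because a patient cannot take both values of one covariate.

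**Working it through.** **Inputs.** Both definitions come from SAP 2.3.4, with the first repeated in 2.4.4.1. The number randomized is 118 (SAP section 1: "A total of 118 patients (out of 280 planned patients) have been randomized in the study"). Neither document says how many patients were impacted, and the plan gives no figure of its own to reproduce.

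**Logic.** Let D mean a critical or major COVID-19 deviation and T mean permanent treatment discontinuation due to COVID-19.

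- With impact: D or T.
- Without impact, as written: (not D) or (not T), which equals not (D and T).
- Complement of with impact: not (D or T), which equals (not D) and (not T).

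| D | T | With impact | Without, as written | Without, using 'and' |
|---|---|---|---|---|
| no | no | no | yes | yes |
| yes | no | yes | yes | no |
| no | yes | yes | yes | no |
| yes | yes | yes | no | no |

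As written, rows two and three sit in both populations, and only patients with both D and T leave the unaffected group. With 'and', nobody is in both groups and nobody is left out.

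**Size.** Let a patients have D only, b have T only and c have both, with N = 118.

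- With impact = a + b + c
- Without, as written = N − c
- Counted twice = a + b
- Without, using 'and' = N − (a + b + c)

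The trigger is more than 0.10 × 118 = 11.8, so at least 12 patients, taking the randomized patients as the denominator (the SAP does not name one). The counts a, b and c below are assumptions.

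| a, b, c | With impact (%) | Without, as written | Sum of the two | Counted twice | Without, using 'and' |
|---|---|---|---|---|---|
| 0, 2, 0 | 2 (1.7) | 118 | 120 | 2 | 116 |
| 12, 0, 0 | 12 (10.2) | 118 | 130 | 12 | 106 |
| 12, 2, 1 | 15 (12.7) | 117 | 132 | 14 | 103 |
| 24, 2, 2 | 28 (23.7) | 116 | 144 | 26 | 90 |

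The first row stays below the trigger, so no split would be produced. The overlap is zero only if every impacted patient meets both criteria. If none meets both, the unaffected group as written is the whole trial.

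**The case against.** The strongest reply is that nobody would program it this way. The sentence directly after the faulty one defines the impacted population without ambiguity. Sections 1.6 and 2.4.4.1 then call for a Yes/No flag, and once Yes is fully defined, No is everyone else. The interaction model forces one level per patient. Loose English also plays a part, since a phrase such as 'without A or B' normally means neither.

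Most of this stands. The intent can be inferred, and that limits the severity. The appeal to ordinary English is weaker, because the second condition carries its own negation: the sentence joins two negatives with 'or', and it does so in both places. Neither document contains an 'and' version or a rule for patients who meet both definitions.

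The reach is also narrow, and that stands in full. COVID-19 impact is one of eleven subgroup factors, subgroup results carry no alpha under section 2.4.4.4, and the outputs depend on the 10% condition. Several COVID-19 summaries do not use these populations: disposition by visit, deviations by COVID-19 impact, discontinuations for COVID-19 reasons and COVID-19 adverse events.

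A reader might also infer that the wording leaves the trigger itself undecided, because 2.4.4.1 states only the negative definition, and its complement would count only patients meeting both criteria. The documents do not support that: the trigger counts impacted patients, and 2.3.4 defines those directly.

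**Conclusion.** The definition is wrong as written, and the severity is minor. Followed literally, it puts every patient who meets exactly one criterion into both populations, against the SAP's own Yes/No variable and interaction model. The logical fault rests on no assumption. Its size rests on counts that the documents do not give: above the trigger, the illustrations run from 12 to 26 patients counted twice.

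A reader might infer that the primary conclusion is at risk. It is not. The primary test is Fisher's exact test in the intent-to-treat population, and the next test in the hierarchy compares total cumulative corticosteroid dose; neither uses these populations. Nor do the documents show that overlapping tables will actually be produced, since the adjacent definition points to the intended split and the outputs appear only if the 10% condition is met.

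**What to change.** In SAP sections 2.3.4 and 2.4.4.1, change the 'or' that joins the two negated conditions to 'and', leaving the 'or' in the deviation grading alone. A patient without impact is then one with no critical or major COVID-19 deviation and no permanent treatment discontinuation due to COVID-19, which is the exact complement of the existing definition of impact.

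The cost is one word in two places. It needs no new data, leaves the definition of the impacted population and the 10% condition as they are, and changes no other analysis.

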2.4 STATISTICAL METHODS

2.4.1 Demographics and baseline characteristics

Continuous data will be summarized using the number of available data, mean, standard deviation (SD), median, minimum, and maximum for each treatment group. Categorical and ordinal data will be summarized using the number and percentage of patients in each treatment group.

Parameters will be summarized based on the randomized populations.

Parameters described in [Section 2.1.1](#) will be summarized by treatment group and overall using descriptive statistics.

Medical and surgical history will be summarized by SOC and PT sorted by internationally agreed order of SOC and by the decreasing frequency of PT within SOC in total group (including all the randomized patients). P-values on demographic and baseline characteristic data will not be calculated.

No specific description of the safety parameters will be provided at baseline. If relevant, the baseline values will be described along with each safety analysis.

2.4.2 Prior or concomitant medications

The prior and concomitant medications will be summarized based on the randomized populations as follows:

- Prior medications discontinued before the first dose of IMP in the DB period
- Prior medications that continued at the time of the first dose of IMP in the DB period
- Concomitant medications

Medications will be summarized by treatment group according to the WHO-DD dictionary, considering the first digit of the anatomic category (ATC) class (anatomic category) and the generic names. All ATC codes corresponding to a medication will be summarized. Patients will be counted once in each ATC category (anatomic or therapeutic) linked to the medication; therefore, patients may be counted several times for the same medication.

In addition, the following summaries will also be provided:

- Vaccines (prior)
- Other prior DMARDs/immunosuppressive agents taken since diagnosis of PMR and discontinued before the first dose of IMP

The table for prior medications will be sorted by decreasing frequency of anatomic category followed by all other generic names based on the overall incidence across treatment groups. In

case of equal frequency regarding anatomic categories (respectively, generic names), alphabetical order will be used.

The tables for concomitant medications will be sorted by decreasing frequency of anatomic category followed by all other generic names based on the incidence of the total group (including all the randomized patients). In case of equal frequency regarding anatomic categories (respectively, generic names), alphabetical order will be used.

2.4.3 Extent of investigational medicinal product exposure and compliance

The extent of SC IMP exposure and compliance will be assessed and summarized by actual treatment group within the safety population and in populations with and without trial impact due to COVID-19 ([Section 2.3.2](#) and [Section 2.3.4](#)).

2.4.3.1 Extent of investigational medicinal product exposure

The extent of SC IMP exposure will be assessed by the duration of SC IMP exposure and actual dose information.

The duration of SC IMP exposure is defined as last DB dose date – first DB dose date +14 days, regardless of unplanned intermittent discontinuations (see [Section 2.5.3](#) for calculation in case of missing or incomplete data). Duration of SC IMP exposure will be summarized descriptively as a quantitative variable (number, mean, SD, median, minimum, and maximum). In addition, duration of treatment exposure will also be summarized categorically by numbers and percentages for each of the following categories and cumulatively according to these categories: ≤ 4 weeks, >4 and ≤ 8 weeks, >8 and ≤ 12 weeks, >12 and ≤ 16 weeks, >16 and ≤ 20 weeks, >20 and ≤ 24 weeks, >24 and ≤ 32 weeks, >32 and ≤ 40 weeks, >40 and ≤ 52 weeks and >52 weeks. The cumulative duration of treatment exposure, defined as the sum of patients' duration of treatment exposure and expressed in patient years, will also be provided.

2.4.3.2 Compliance

A given administration will be considered noncompliant if the patient did not take the planned dose of treatment as required by the protocol. No imputation will be made for patients with missing or incomplete data.

Percentage of compliance for SC IMP will be defined as the number of administrations the patient was compliant divided by the total number of administrations the patient was planned to take on or before the last dose date during the DB treatment period.

Percentage of compliance for oral IMP compliance rate will be defined as the total number of days patient with partial or complete oral IMP intake divided by total number of days between the first oral IMP intake date and day prior to rescue therapy start date or EOT date which is earlier.

Treatment compliance percentages will be summarized descriptively as quantitative variables (number, mean, SD, median, minimum, and maximum). The percentage of patients whose compliance is $<80\%$ will be summarized.

Cases of overdose (administering two or more doses of sarilumab or its matching placebo in less than 11 calendar days) will constitute AESI and will be listed as such. More generally, dosing irregularities will be listed in [Section 2.2.1](#).

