The daily encapsulated dose may contain prednisone, placebo, or a combination of the two. The number of tablets to be taken each day will vary but will not be consistent with the dosage of prednisone. The number of tablets to be taken daily may increase or decrease during the tapering schedule but will not exceed 6 tablets per day.

In the later stages of the study where visits are more than 1 month apart, an interim visit may be required for IMP dispensing between protocol scheduled on-site visits. As an alternative to these visits, prednisone may be supplied from the site to the patient via a sponsor-approved courier company where allowed by local regulations and approved by the subject.

Refer to [Appendix A](#) for detailed standardized CS taper regimen during the double-blind study treatment period.

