### 8.7.1 Treatment accountability and compliance

Measures taken to ensure and document treatment compliance and IMP accountability include:

- Proper recording of treatment kit number or packaging number as required on appropriate electronic case report form (eCRF) page for accounting purposes;
- All medication treatment kits for sarilumab or matching placebo (whether empty or unused) are returned by the patient at each visit when a treatment dispensing is planned.
  - Except for the prefilled syringes that cannot be safely returned to the study site after administration of IMP, the completed patient injection diary (returned to the site at each visit), returned treatment kit boxes and any unused prefilled syringes will be used for drug accountability purposes.
- All packs of prednisone treatment (whether empty or unused) are returned by the patient at each visit when a treatment dispensing is planned.
- The study coordinator tracks treatment accountability/compliance, either by diary, or by counting the number of used treatment kits/tablets/capsules and fills in the appropriate page of the patient treatment log.

The monitor in charge of the study then checks the data entered on the IMP administration page by comparing them with the IMP that has been retrieved and the patient treatment log form.

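### Oral study-drug compliance (SAP 2.4.3.2) scores a partial-intake day as fully compliant, so partial intake on every day is reported as 100% and never falls below the 80% line

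*SAP*

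**What the plan says.** SAP 2.4.3.2 opens with a rule that is not limited to either product: "A given administration will be considered noncompliant if the patient did not take the planned dose of treatment as required by the protocol". The injection formula follows it, dividing compliant administrations by planned ones. The oral formula is different. It is the "total number of days patient with partial or complete oral IMP intake divided by total number of days", the days being counted "between the first oral IMP intake date and day prior to rescue therapy start date or EOT date which is earlier". For the resulting percentages, "The percentage of patients whose compliance is" below 80% is to be tabulated. Protocol 11.4.1.2 defines compliance for injections only, so this SAP line is the only definition for the oral drug.

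Protocol 8.1.2 describes the oral drug as over-encapsulated 1 mg or 5 mg tablets, or placebo. The daily count "will not exceed 6 tablets per day". The protocol adds: "The number of tablets to be taken each day will vary but will not be consistent with the dosage of prednisone". The planned count for each day is not given. Under protocol 8.7.1, compliance is tracked either from the diary or "by counting the number of used treatment kits/tablets/capsules".

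**The concern.** The two arms differ in steroid taper as well as in drug, so taking the oral study drug is part of delivering the intervention. A compliance table should show how far that happened. As defined, this one detects only days on which nothing was taken. A patient who regularly leaves out part of the day's capsules looks identical to one who takes them all.

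This would matter less if another planned summary measured under-intake. Two look as if they might, and neither does:

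- Component 4 of the primary endpoint (SAP 2.1.3.1), adherence to the taper, looks at rescue therapy and excess prednisone. It does not count missed capsules.
- The actual cumulative corticosteroid dose (SAP 2.4.4.2) takes its taper contribution from the scheduled regimen, so untaken capsules are credited as taken.

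**Working it through.** The documents state no compliance figure, so there is none to reproduce. The check applies the SAP formula as written and compares it with two alternatives.

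**Inputs.** Oral treatment runs from Week 0 to the end of Week 51 (protocol 8.1.2), which is 52 × 7 = 364 days. The planned number of capsules per day is an assumption, ranged from 2 to the ceiling of 6. No rescue therapy is assumed.

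**Formulas.**
- SAP: 100 × days with any intake / days in period
- Capsule-based: 100 × capsules taken / capsules planned
- Complete-day: 100 × days with all capsules taken / days in period

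**One capsule taken every day.** The SAP figure is 364/364 in every row.

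| Planned per day | SAP | Capsule-based | Complete-day |
|---|---|---|---|
| 2 | 100% | 1/2 = 50% | 0% |
| 3 | 100% | 1/3 = 33.3% | 0% |
| 4 | 100% | 1/4 = 25% | 0% |
| 5 | 100% | 1/5 = 20% | 0% |
| 6 | 100% | 1/6 = 16.7% | 0% |

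**Some days partial (1 of 6), the rest complete (6 of 6).** Planned total: 364 × 6 = 2,184 capsules.

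| Partial days | SAP | Capsule-based | Complete-day |
|---|---|---|---|
| 36 (about 10%) | 100% | (36 + 328 × 6)/2,184 = 91.8% | 328/364 = 90.1% |
| 91 (25%) | 100% | (91 + 273 × 6)/2,184 = 79.2% | 273/364 = 75.0% |
| 182 (50%) | 100% | (182 + 182 × 6)/2,184 = 58.3% | 182/364 = 50.0% |

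At 25% partial days both alternatives fall below 80%. The SAP figure does not move.

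**Dose on one day.** Both tapers prescribe 14 mg/day in Week 2 (protocol Appendix A). With 5 mg and 1 mg units and at most six of them, this can only be 2 × 5 + 4 × 1 = 14 mg, all active. One capsule then carries between 1/14 = 7.1% and 5/14 = 35.7% of the day's dose, and the day scores as compliant.

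**What the cumulative dose credits.** Summing Appendix A over weeks gives 7 × 111 = 777 mg for Group 1 and 7 × 292 = 2,044 mg for Group 2, a difference of 1,267 mg. For patients who complete treatment with no add-on, rescue or commercial steroid, these scheduled amounts enter the actual dose whatever was swallowed.

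**The case against.** Several points on the other side stand.

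- **The percentage drives nothing.** It feeds no endpoint, test, analysis population or decision rule. A reader might infer that a patient taking one capsule in six is being counted as adherent in the primary endpoint because of this formula. That is not so: component 4 has its own definition and does not use the percentage.
- **Missed capsules do not create a steroid-sparing result.** A reader might also infer that hidden under-intake could lower the cumulative dose. It cannot, because the taper contribution is taken from the schedule. Changing the compliance formula would leave that endpoint unchanged.
- **The error is not strictly one-way.** Partial days always push the figure up. But the denominator is calendar days, with no imputation, so unrecorded days and permitted interruptions of the oral drug can push it down.
- **The extreme case is rare by design.** Six capsules is a ceiling, and 14 mg/day applies to 7 of 364 days. Group 1 takes only placebo capsules in Weeks 14 to 51, 38 of 52 weeks, when a missed capsule removes no prednisone. The documents give no frequency of partial days.
- **Other routes exist.** SAP 2.2 summarises critical and major deviations, and site staff and monitors check compliance. The documents do not say whether oral under-intake is a deviation category, so this table is the main defined place for it to appear, not demonstrably the only one.
- **Capsule counts are not guaranteed.** Protocol 8.7.1 allows diary or counts, and counts may be at kit level.

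It can also be argued that the opening rule was written for injections: the matching sentence in protocol 11.4.1.2 refers to an injection dose. A programmer would follow the specific oral formula. That explains the mismatch but does not remove it, because the SAP reworded the sentence to cover treatment generally. The oral percentage would still be read as compliance with the planned dose.

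**Conclusion.** The point holds as a reporting defect in one table. Followed exactly, the rule gives 100% to any patient with some intake every day, against a capsule-based figure between 16.7% and 50% when one capsule is taken daily and 2 to 6 are planned. Such a patient can never be flagged below 80%. The result for the SAP formula does not depend on the number planned; the comparison figures do, and they are illustrations, not estimates for this trial.

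The documents do not support saying that the primary analysis or the cumulative-dose test is altered, or that the formula can only overstate compliance. What is lost is the ability to see under-intake of the oral regimen in the main table defined to show it. The change is worth making because it is cheap and the present figure misleads.

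**What to change.** In SAP 2.4.3.2, report complete, partial and no-intake days separately by arm over the existing period, and apply the below-80% category to complete days. State how days without a record are classed. Where capsule counts were actually recorded, add capsules taken divided by capsules scheduled over the same period as a supportive figure. Footnote that capsules mix active and placebo, so neither measure equals the prednisone dose taken.

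**Cost.** New SAP wording and reprogramming of one table. This assumes that partial and complete days are recorded distinguishably, which the SAP's own numerator implies but the documents do not show. According to SAP 1.1 the last patient visit was on 19 May 2021, so missing counts cannot now be collected. Reported compliance will be less favourable, and a patient who misses one placebo capsule will lose that day as complete. Showing partial days separately lets the reader see this.
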